6.2 Eligibility criteria

6.2.1 Inclusion criteria

- Over the age of 18
- VLU¹
- Tolerating compression bandaging
- Able to give consent

6.2.2 Exclusion criteria

- Under the age of 18 years
- Unable to fully understand the consent process and provide informed consent due to either language barriers or mental capacity
- Limited life expectancy, i.e. undergoing palliative care

¹ The case definition for VLU is any break in the skin on the lower leg that has been present for 2 weeks or more with a clinical venous aetiology and an ankle brachial pressure of \geq 0.8 (NICE 2013).

6.3 Early withdrawal of subjects

Patients have the right to withdraw from the trial at any time and without giving any reason. If a patient withdraws from the trial, any and all information gathered prior to the withdrawal will be excluded in the analysis, no further data collection will occur. If a patient does not attend a planned follow-up appointment then two more attempts will be made to contact the patient regarding the study. If still no contact can be made then the patient is deemed lost to follow-up and any collected study data will be retained.

7. SAFETY

7.1 Potential risks & benefits to study participants

There is no anticipated personal safety risk associated with taking part in this study. If the research team learns of important new information that might affect patient's desire to remain in the study, he or she will be told. Appropriate precautions are in place to ensure medical and personal information is kept safe through adhering to appropriate governance regulations. Participants in the StepIt intervention group will be asked to do the StepIt exercise; this will take more time and effort compared to standard management (treatment as usual). Any adverse events will be recorded, as outlined in sections below.

For the participants in the control group there is no direct benefit in taking part in this study. They will be cared for in exactly the same manner as they normally would. For participants in the Step It intervention group, there may be benefits in terms of improved VLU healing compared to normal standard care. However, this has not yet been proven and established, and this study is aimed to assess this. Participants cannot claim payments, reimbursement of expenses or any other benefits or incentives for taking part in this research.

7.2 Safety definitions

Adverse Event (AE)	Any untoward medical occurrence in a patient or other clinical investigation participant taking part in a trial of a medical device, which does not necessarily have to have a causal relationship with the device under investigation.				
	An AE can therefore be any unfavourable and unintended sign (including an abnormal laboratory finding), symptom or disease temporally associated with the use of the device, whether or not considered related to the device.				
Serious Adverse Event	A serious adverse event is any untoward medical occurrence that:				
	- results in death				
	- is life-threatening				
	- -				

- requires inpatient hospitalisation or prolongation of existing hospitalisation
- results in persistent or significant disability/incapacity
- consists of a congenital anomaly or birth defect.

Other 'important medical events' may also be considered serious if they jeopardise the participant or require an intervention to prevent one of the above consequences.

NOTE: The term "life-threatening" in the definition of "serious" refers to an event in which the participant was at risk of death at the time of the event; it does not refer to an event which hypothetically might have caused death if it were more severe.

7.3 Procedures for recording adverse events

All SAEs need to be reported to the sponsor/host Trust R&D within one working day of the investigator team becoming aware of them.

The only device to be in contact with the patient is the sterile swab provided by the hospital and employed by hospital staff only.

The relationship of each adverse event to the trial must be determined by a medically qualified individual according to the following definitions:

- Related: The adverse event follows a reasonable temporal sequence from swabbing. It cannot reasonably be attributed to any other cause.
- **Not Related**: The adverse event is probably produced by the participant's clinical state or by other modes of therapy administered to the participant.

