PREVUE v4, dd 12Dec2018

PREVUE; PlantaR flexion Exercise for Venous Ulcer Evaluation, a multi-centre, controlled, prospective, randomized feasibility trial

Version 4, dd 12 December 2018

Chief Investigator's Statement of Ownership and Content.

I, [name], confirm that this protocol is my work and is owned by me. The protocol conforms with standards outlined in the Declaration of Helsinki 1964.

Name (PRINT):___[name]_____

Signature:

Date: ____12 Decl 2018_____

RESEARCH PROTOCOL SUMMARY

TITLE:	PREVUE; PlantaR flexion Exercise for Venous leg UlcEr, a multi- centre, controlled, prospective, randomized feasibility trial
Short title:	PREVUE
IRAS number	222694
Device description	StepIt plantar flexion rocker pedal device. CE-marked and licensed medical device. To be used in this study for indicated purpose, namely plantar flexion exercise.
Study design	Single centre, controlled, prospective randomized feasibility trial
Primary objective	To assess the feasibility of conducting a full RCT in the future - Participants' compliance to StepIt exercise regime
	 Recruitment and attrition rates, willingness of patients to be randomised, response rates to questionnaires, and degrees of missing data Testing of eligibility criteria and ability/willingness of clinical staff to partake in recruitment of participants Adequacy of duration of follow-up (e.g. in relation to VLU healing)
Secondary objectives	To determine the acceptability and efficacy of the step-it pedal as an adjuvant therapy for VLU at 6 and 12 weeks post-baseline - Healing rate (ulcer size, PUSH score) - Ankle motion range - Patient mobility score - VLU-related quality of life score - VLU-related pain - Patient feedback on use of the device
Patient population	A total of 28 participants, over the age of eighteen, with venous leg ulcers and treated either in hospital or at home by the community nursing team. Participants must have the capacity to provide informed written consent and complete patient reported outcome measures. Participants are recruited from the local community nursing caseload and identified in hospital clinics. - 12 Patient will receive treatment as usual (TaU) - 12 Patients will receive TaU plus StepIt exercise programme intervention

	Randomisation will be stratified for ulcer size, with cut-off PUSH
	score of up to 8, and 9 and above.
Sponsor	Cumbria Partnership NHS Foundation Trust
Manufactures O foundan	Charalle Coreboure A.D.
Manufacturer & funder	StepIt System AB,

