Participants will be randomised to either the control group (standard care) or the intervention group (standard care plus use of a StepIt pedal) for 12 weeks or until ulcer healing has taken place. Patients in both groups will be given the usual leg ulcer information leaflet, but those in the intervention group will be issued with a StepIt Pedal to use daily for foot and ankle exercises. These exercises consist of resisted plantar flexion while seated, performed 2 times daily in the pattern of: 1 minute exercise / 1 minute rest, 10 times (participants may alternate legs as an alternative to merely resting both legs for 1 minute). The participants will be asked to keep an exercise diary to record their activity. At their discharge visits participants are asked to provide their opinion on trial participation. All participants will have demographic data obtained and the following base line measures (table 2):

- VLU size measured with Convatec grid tool
- PUSH score (size and characteristics)
- Mobility score
- Ankle range of motion using a goniometer
- Visual analogue pain score
- Quality of life assessment using the Charing Cross Venous Ulcer Questionnaire

Table 3. Baseline measures

Weeks	0	2	4	6#	8	10	12#
Ulcer size and PUSH score	Х			Χ			Χ
Mobility score	Χ			Х			Χ
Ankle range of motion	Χ			Х			Χ
Visual analogue pain score	Χ			Χ			Χ
Charing Cross Venous Ulcer Questionnaire	Х			Х			Χ

Allowed to be up to 2 weeks early or late

The Pressure Ulcer Scale for Healing (PUSH) tool, see Appendix 1 is a standardised method of assessing and monitoring the severity and healing of both pressure ulcers and venous leg ulcers (Stotts et al, 2001; Ratliff & Rodeheaver 2005). Concerns have been raised regarding the criterion validity and intra-rater reliability of the tool (Pillen et al 2009) however in the absence of other valid tools it provides a comprehensive parallel assessment of the ulcer along with measuring size alone.

A mobility measure will be taken using a life space questionnaire, see Appendix 1 (Stalvey *et al* 1999). This is a tool that has demonstrated reliability and construct and criterion validity in establishing the spatial extent of an older person's mobility within their home setting. There are other versions (Peel *et al* 2005) that additionally measure the use of aids and equipment however this is not of particular interest within the study, hence the simpler version will be used.

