8.2 Primary outcome statistics

The primary objective for this pilot study is the feasibility of conducting a larger scale randomised controlled trial. The secondary outcome statistics will inform the success of this pilot study and will therefore inform whether a larger scale trial is indicated. This will be based on signs of clinical effectiveness, positive patient feedback on the intervention, positive changes in VLU related quality of life, recruitment to time and target, low attrition rates, minimal data queries and lack of or low number of adverse events. If the effect size of the Steplt pedal is large enough, then this pilot trial may provide a definitive answer concerning its clinical effectiveness.

The following descriptive statistics will be reported on:

- Number of patients screened
- Number of patients eligible/ineligible, and percentage of patients consented into the trial
- Number of patients completed the trial/discontinued (plus reasons if discontinued)

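### Section 7.3 ties adverse-event causality to swabbing, which is not this trial's intervention, so the related / not related label cannot be applied properly to the StepIt pedal

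*Protocol*

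**What the plan says.** Protocol section 7.3 (Procedures for recording adverse events) makes the causality rule binding: "The relationship of each adverse event to the trial must be determined by a medically qualified individual according to the following definitions". Two classes follow.

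- **Related** has two conditions: "The adverse event follows a reasonable temporal sequence from swabbing", and "It cannot reasonably be attributed to any other cause".
- **Not Related** has one: "The adverse event is probably produced by the participant's clinical state or by other modes of therapy administered to the participant".

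Just before these definitions the section states: "The only device to be in contact with the patient is the sterile swab provided by the hospital and employed by hospital staff only".

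The rest of the protocol describes a different device. The Research Protocol Summary names it as "StepIt plantar flexion rocker pedal device", and section 3 describes the same pedal. Under section 5.3, "those in the intervention group will be issued with a StepIt Pedal to use daily for foot and ankle exercises". Section 7.2 defines adverse events by reference to the device under investigation.

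Adverse events are one of the primary outcome measures in section 5.5.1. Section 8.2 lists "lack of or low number of adverse events" among the signs that would support a larger trial.

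**The concern.** The causality rule names the wrong exposure. It asks the assessor to judge each event against a procedure that is not part of the intervention, and it describes a device handled by hospital staff when the pedal is handled by the patient. The sentences are complete and legible, so neither redaction nor faulty text extraction explains them. They look like text carried over from another study. The mention in section 5.2 of consent being taken by a continence care team points the same way.

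What is at stake is the trial's record of which events the pedal may have caused. Section 2 says that this is the first use of the pedal in patients with venous leg ulcers, section 3 says that its resistance cannot be adjusted, and section 7.1 anticipates no personal safety risk. Event-by-event attribution is one of the ways to test that last statement. Section 9 provides for in-house monitoring and no trial steering committee, so the protocol names no outside group that would notice a misapplied label.

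**Working it through.** No arithmetic applies. The check sets the sections side by side and then runs the possible kinds of event through the two definitions.

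**Step 1: is the swab part of this trial?**

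| Place in protocol | What it describes |
|---|---|
| Summary; section 3 | StepIt rocker pedal as the device |
| 5.3, with the table of measures | Pedal exercises, ulcer measurement, questionnaires, goniometer; no swab |
| 5.4 | Routine redressing and ulcer measurement, research visits; no swab |
| 5.5 | Outcomes, including ulcer infection rates; no swab |
| 7.2 | Events defined by reference to the device under investigation |
| 7.3 | Sterile swab as the only device; causality judged from swabbing |

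Section 7.3 stands alone and conflicts with the summary and with sections 3, 5.3 and 7.2.

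**Step 2: apply the definitions as written.** Related needs a plausible time sequence from swabbing (call this T) and no other reasonable cause (call this N). Not Related needs clinical state or other therapy to be the probable cause (call this P).

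1. *Event caused by the pedal, participant never swabbed.* T fails, so the event is not Related. P is met only if the pedal counts as one of the other modes of therapy. With swabbing as the reference exposure, that is a natural literal reading, and it labels a device-caused event Not Related. If the pedal is not read that way, the event has no class.
2. *Event caused by the pedal, participant happened to be swabbed in routine wound care.* T may be met, but N fails because the pedal is itself a reasonable other cause. The outcome is the same as in case 1.
3. *Event probably due to the participant's clinical state.* P is met and the event is Not Related. The rule works here.

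**Step 3: substitute the pedal for swabbing and test again.**

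4. *Event plainly due to the exercise.* T and N are met, so it is Related. This repairs cases 1 and 2.
5. *Event after exercise, with another cause that is reasonable but not probable.* N fails, so it is not Related. P fails, so it is not Not Related either. It has no class.

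Case 5 shows that changing the exposure alone is not enough, because the two definitions are not complements of each other.

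**Step 4: what depends on the label?** Section 7.1 has any adverse event recorded. Section 7.2 counts an event whatever view is taken of its link to the device. Section 7.3 requires all serious events to be reported within one working day, without regard to causality. Section 5.5.1 lists adverse events without qualification, and the criterion in section 8.2 refers to their number, not to the number judged related. None of these uses the faulty definition.

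**The case against.** The strongest reply is that the lead-in asks about the relationship to the trial and leaves the judgement to a medically qualified assessor, and that section 7.2 already points to the device under investigation. A sensible assessor could simply read pedal for swab. That softens the practical effect, but the written definition does not authorise the substitution, assessors may differ in whether they make it, and it does not close the gap in case 5.

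A second reply is that swabbing might occur, since ulcer infection is an outcome and its method of ascertainment is not stated. That is fair as far as it goes: the protocol can only be said to describe no swabbing elsewhere, not to exclude it. It does not rescue the rule, as case 2 shows.

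A third reply concerns reach, and it stands. A reader might infer that a primary outcome and the criterion for a larger trial are compromised, or that the trial has no ability to detect harm from the pedal. The documents do not support either. Both uses of adverse events are worded in terms of all events. A difference between the randomised arms in all events could still be seen whatever individual labels were given.

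**Conclusion.** The concern holds as a defect in causality classification. The mandatory rule in section 7.3 names an exposure that contradicts the summary and sections 3, 5.3 and 7.2, and taken literally it prevents a pedal-caused event from being classed as related. Separately, the two classes do not cover all events.

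Its reach is every related / not related call made under section 7.3 and nothing beyond. Total event counts, serious-event reporting and comparisons of all events by arm are intact. No numerical size can be attached: that a pedal-caused event cannot be Related follows from the literal wording, and is not an estimate of how assessors behaved.

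The conclusion assumes that the definitions are applied as written and that the text available for review is representative on this point. Whether any event has already been classified under this wording is not known from the protocol.

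**What to change.** Amend section 7.3 as follows.

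- Delete the sentence about the sterile swab.
- Define relatedness to use of the StepIt pedal and the StepIt exercise programme, so that section 7.3 agrees with sections 3 and 7.2.
- Word the two classes so that every event falls in one of them, for example by making Not Related whatever does not meet Related. Where to set the threshold for Related is for the sponsor to decide. Treating a reasonable possibility of a device cause as Related is one convention, and the documents do not prescribe any.
- Re-assess the causality of any event already classified under the swab wording. Version 4 is dated 12 December 2018 and section 5.1 planned recruitment from May 2017 to December 2018, so such events may exist.

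The cost is a one-paragraph amendment with its usual review and, if events have been logged, a short second look at them. No new data, visits or participants are needed.

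### Section 7.3 ties adverse-event relatedness to swabbing, which the protocol does not otherwise describe, so the related/not-related classification cannot identify an event caused by the StepIt pedal

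*Protocol*

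**What the plan says.** Section 7.3 sets a binding rule for causality: "The relationship of each adverse event to the trial must be determined by a medically qualified individual according to the following definitions". Two classes follow.

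- *Related* has two limbs. The first is: "The adverse event follows a reasonable temporal sequence from swabbing". The second requires that no other cause can reasonably explain the event.
- *Not Related* reads: "The adverse event is probably produced by the participant's clinical state or by other modes of therapy administered to the participant".

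Just before these definitions, the section states: "The only device to be in contact with the patient is the sterile swab provided by the hospital and employed by hospital staff only".

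The rest of the protocol describes a different exposure. The Research Protocol Summary names the device as the "StepIt plantar flexion rocker pedal device". Section 3 describes the pedal. Section 5.3 (Recruitment) says that "those in the intervention group will be issued with a StepIt Pedal to use daily for foot and ankle exercises". Section 6.1.1 treats the intervention as self-administered.

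Section 7.2 defines an adverse event independently of cause, as an occurrence "whether or not considered related to the device". Section 5.5.1 lists adverse events among the primary outcome measures. Section 8.2 includes among the signs of a successful pilot "minimal data queries and lack of or low number of adverse events".

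**The concern.** A causality rule has to name the exposure whose effects it is meant to detect. Here it names one that the trial does not describe. The swab sentence conflicts with the rest of the protocol on which device is meant, on its being the only one, and on who uses it. The text looks carried over from another study.

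Attribution of harm to the pedal is at stake. The Introduction says that this is the pedal's first use in patients with venous leg ulcers, so whether an event is attributable to the device is worth knowing. The researcher is not blinded (section 6.1.1). Monitoring is in-house and no trial steering committee will be convened (section 9), so the protocol describes no independent body that would catch a misclassification.

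**Working it through.** No arithmetic underlies the main point. The check sets the sections side by side and applies the rule as written.

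**1. Is there any swabbing in the trial?** In the available text, swabs and swabbing occur only in section 7.3. The procedures in sections 5.3 and 5.4 and in Table 3 are the grid measurement of the ulcer, the PUSH score, goniometry, a pain scale and questionnaires, alongside routine redressing. None is a swab.

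**2. Apply the rule to an event caused by pedal exercise.**

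- *Related*, first limb: the event must follow swabbing. The protocol describes none, so the limb fails.
- *Related*, second limb: if swabbing is the reference exposure, the pedal is itself another cause, so this limb fails too.
- *Not Related*: the event is not produced by the participant's clinical state. It fits only if pedal exercise counts as another mode of therapy.

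The event therefore either fits neither class or is moved into *Not Related*. Under a literal reading, the number of events classed as related to the pedal is zero, whatever the pedal does. If assessors set the text aside and use their own judgement, the classification has no stated definition and depends on the assessor.

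**3. Trace what depends on the label.**

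| Item | Section | Uses relatedness? |
|---|---|---|
| Capture of adverse events | 7.1, 7.2 | No: any event, whatever its cause |
| SAE report within one working day | 7.3 | No: all SAEs |
| Primary outcome measure | 5.5.1 | No: adverse events without qualifier |
| Success consideration | 8.2 | No: number of adverse events |
| *Related* / *Not Related* class | 7.3 | Yes |

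Only the last row is invalid.

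**4. Size of the affected arm.** The protocol gives more than one sample size.

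- The Research Protocol Summary and Table 4 list 12 patients for StepIt.
- The same two places give a total of 28, and section 6.1 gives 1:1 allocation: 28 / 2 = 14.
- The Lay Summary gives 24 of a total of 48.

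The range is 12 to 24 patients, each in the study for up to 12 weeks.

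**The case against.** The strongest reply is that little depends on the label. Events are captured whatever their cause, every SAE is reported, and the section 8.2 consideration counts events, not related events. With a randomised control arm, harm from the pedal can still appear as a difference in adverse events between arms. No tabulation, reporting rule or stopping rule in the available text uses relatedness. The device is also CE-marked and used for its indicated purpose. All of this stands, and it confines the point to the classification. A reader might infer from the listing of adverse events as a primary outcome measure that this outcome, or the decision to go on to a larger trial, is wrong by construction. The documents do not support that.

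A second reply is that a medically qualified assessor asked about relationship to the trial would recognise the misplaced text and judge against the pedal. That may happen, so zero related events is the result of the literal reading and not a forecast. But the protocol tells the assessor to use the stated definitions, and a rule that works only when ignored still needs correcting.

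A third reply is that wound swabs may be taken in routine care, since section 5.5.2 lists ulcer infection rates. The protocol does not say so. If it did, swabbing would still be the wrong reference exposure for a trial of a pedal.

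It is also tempting to say that sections 7.2 and 7.3 give three competing rules: relation to the device, to the trial and to swabbing. Section 7.2 mentions the device only to say that causality is not needed for an event to count. The clash is within section 7.3, between the trial and swabbing.

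**Conclusion.** The point holds in a limited form. Section 7.3 is wrong as written: its definition of *Related* and its statement about the only device in contact contradict the Research Protocol Summary and sections 3 and 5.3. Read literally, it lets no pedal-caused event be classed as *Related*, so the related/not-related classification is invalid. It affects the attribution of events in the StepIt arm, 12 to 24 patients. Total adverse-event and SAE counts by arm, SAE reporting and the section 8.2 consideration remain sound.

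Two assumptions underlie this. One is that assessors follow the definitions as worded. The other is that no swabbing is described in the parts that could not be read, which are some text near the front and the flowcharts in Appendices 2 and 3. This is an internal inconsistency and not a missing detail that an analysis plan could supply, because the protocol itself fixes the definition.

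**What to change.** Reconcile section 7.3 with the Research Protocol Summary and sections 3, 5.3 and 7.2:

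- Delete the sentence naming the swab as the only device in contact with the patient.
- In the definition of *Related*, replace swabbing with use of the StepIt pedal, as the device under investigation, or with participation in the trial.
- Re-read any adverse events already classified, using the corrected definition.

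The cost is a protocol wording amendment, a matching change to the adverse-event form if it repeats the text, and the time to re-read recorded events. No extra patients, visits or measurements are needed.
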